9.3. Recording and reporting of SAEs, SARs AND SUSARs

AEs will be recorded on the AE Log in the eCRF and will be assessed for severity and causality by the CI or PI. AEs occurring from the time a participant consents to join the trial until the participant's day 29 will be recorded. An AE may be classified as a SAE or AR. An initial assessment of expectedness/listedness for SAEs will be conducted by the PI based on the Reference Safety Information (RSI).

Participants discharged from hospital before the end of trial will be given a diary to record adverse events, this will be used as an aide memoire for them to report AEs at the telephone follow-up call. This diary will not be returned to the trial staff.

The PI will make a clinical judgment as to whether or not an AE is of sufficient severity to require the participant's discontinuation of treatment. A participant may also voluntarily discontinue treatment due to what he or she perceives as an intolerable AE. If either of these occurs, the participant should be given appropriate care under medical supervision until symptoms cease, or the condition becomes stable.

AEs and SAEs will be followed up until recovered/recovered with sequelae/death or for 30 days after participant's day 29 whichever happens first. SUSARS will be followed until resolution.

The CI, PI or delegate will check the medical records for the occurrence of AEs and hospitalisations at every data collection point/telephone call during the trial. Serious AEs (SAEs) will be submitted on an SAE form to the Sponsor Pharmacovigilance Section [contact] within 24 hours

of becoming aware of the SAE. All SAEs need to be assessed and signed off by the PI or a delegated doctor within the 24hr reporting window. Site PIs will also notify the CI when submitting an SAE.

The evaluation of expectedness will be made based on the knowledge of the reaction and the relevant safety information (RSI) in the Brensocatib Investigators Brochure (IB) (see section 9.4). The Sponsor will make the definitive assessment on expectedness for the purposes of SUSAR reporting.

The Sponsor is responsible for reporting SUSARs to the UK competent authority, the MHRA, and the Research Ethics Committee (REC). Fatal or life threatening SUSARs will be reported within 7 days and non-fatal and non-life threatening SUSARs within 15 days.

9.4. Reference Safety Information

RSI is described in Section 6.6 of the IB. The RSI is used to assess the expectedness of events and will be checked by the CI for changes on the anniversary of the issue date of the CTA. Any change to the RSI for the IMP will be reviewed and if it changes significantly this may result in a substantial amendment to submit the updated IB.

9.5. Responsibilities

Principal Investigator (PI):

- Checking medical records for AEs and ARs.
- Using medical judgement in assigning seriousness, causality and whether the event/reaction was anticipated using the approved Reference Safety Information.
- · Confirmation of eligibility criteria

Chief Investigator (CI) / delegate:

- Clinical oversight of the safety of participants participating in the trial, including an ongoing review of the risk / benefit.
- Using medical judgement in assigning the SAEs seriousness, causality and whether the event
 was anticipated (in line with the Reference Safety Information) where it has not been possible to
 obtain local medical assessment.
- Review of specific SAEs and SARs in accordance with the trial risk assessment and protocol.
- Assigning Medical Dictionary for Regulatory Activities (MedDRA) to all SAEs and SARs.
- Preparing the clinical sections and final sign-off of the Development Safety Update Report (DSUR).
- Central data collection and verification of AEs, ARs, SAEs, SARs and SUSARs according to the trial protocol onto a database.
- Reporting safety information to the independent oversight committees identified for the trial (DMC).
- Notifying PIs of SUSARs that occur within the trial.
- Checking for (annually) and notifying PIs of updates to the Reference Safety Information for the trial.

Sponsor:

- Immediate review of all SUSARs.
- Expedited reporting of SUSARs to the Competent Authority (MHRA in UK) and REC within required timelines.

 Preparing standard tables and other relevant information for the DSUR in collaboration with the CI and ensuring timely submission to the MHRA and REC.

Data Monitoring Committee:

In accordance with the Trial Terms of Reference for the DMC, periodically reviewing overall safety data to determine patterns and trends of events, or to identify safety issues, which would not be apparent on an individual case basis. The DMC will also advise on continuation/discontinuation of the trial at these reviews.

9.6. Notification of deaths

All deaths will be reported to the sponsor irrespective of whether the death is related to disease progression, the IMP, or an unrelated event. Reporting of deaths will follow the SAE reporting process and will be reported within 24 hours of the PI or delegate becoming aware of the death.

9.7. Pregnancy reporting

All pregnancies within the trial (either the trial participant or the participant's partner, with participants consent) will be reported to the CI and the Sponsor using the relevant TASC Pregnancy Notification Form within 24 hours of notification. The TASC Pregnancy Notification Form will be submitted to the Sponsor Pharmacovigilance Section [contact]. The pregnancy will be followed up until the end of the pregnancy. If the trial participant is a male, informed consent for follow-up will be sought from his female partner.

Pregnancy is not considered an AE unless a negative or consequential outcome is recorded for the mother or child/foetus. If the outcome meets the serious criteria, this would be considered an SAE

9.8. Overdose

An overdose will be defined as taking more than 50mg of trial medication in a 24-hour period.

Whilst in hospital, the trial medication will be held and given to participants as per drug record by the clinical team. On discharge from hospital, participants will take home enough medication to complete 28 days of treatment.

An overdose itself is not an AE. However, if the overdose results in clinical signs and symptoms, it requires expedited reporting as if it is an SAE. In the case of an overdose, the PI or delegate should use clinical judgment in treating the overdose, and inform the Sponsor immediately.

9.9. Reporting urgent safety measures

The CI, PI or delegate will take appropriate immediate urgent safety measures in order to protect the participants against any immediate hazard to their health or safety. If any urgent safety measures are taken, the CI/Sponsor shall immediately and in any event no later than 3 days from the date the measures are taken, give written notice to the MHRA and the relevant REC of the measures taken and the circumstances giving rise to those measures.

9.10. The type and duration of the follow-up of participants after adverse reactions (AR).

Participants with unresolved ARs at end of trial will be followed up until 30 days after participant's day 29. Suspected Unexpected Serious Adverse Reactions (SUSARs) will be followed up until resolution. Any

SUSAR will be reported to the Sponsor irrespective of how long after IMP administration the reaction has occurred.

9.11. Development safety update reports

The DSUR will be prepared jointly by the Sponsor Pharmacovigilance Section and CI and submitted by the Sponsor to the MHRA on the anniversary of the date of Clinical Trial Authorisation (CTA).

The DSUR and reports of SUSARs in the UK, with an HRA CTIMP Safety Report Form, will be sent to REC by the Sponsor Pharmacovigilance Section. Any other safety reports, for example, reports of a DMC, will be sent by the CI to REC, with a Safety Report Form, and to the Sponsor.

10. STATISTICS AND DATA ANALYSIS

10.1. Sample size calculation

In accordance with the WHO multicentre adaptive trial design recommendations, this trial is intended to allow for adaptation of blinded confirmation or modification of the primary endpoint³³. A brief summary is provided here. Details will be described in the interim evaluation analysis plan.

Blinded endpoint confirmation or modification

The current plan is to evaluate the primary endpoint up to day 29. Because there is uncertainty about the clinical course and potential different trajectories according to baseline disease severity, the day of the primary endpoint may be modified based on a blinded evaluation of various time points (e.g., days 7-29). [Posch, 2012] This will occur by a blinded evaluation by the statistician and trial steering committee without knowledge of treatment assignment.

The primary outcome uses an ordinal severity scale with 7 categories. The null hypothesis being tested is whether the odds of improvement on the ordinal scale is the same for the placebo and experimental treatment arms (i.e., whether the common odds ratio differs from 1).

The proportions of participants in the different categories of the ordinal scale at day 29 in the placebo and treatment arm assuming an odds ratio (OR) of 2 are given below. The odds ratio represents the odds of improvement in the ordinal scale for treatment relative to placebo control [Whitehead, 1993]

Table 4 displays four scenarios considered for outcomes under placebo for sample size determination. There is significant uncertainty with these assumptions given the limited data available.

Table 5 shows a range of sample sizes for odds ratios ranging from 1.5 to 2.5 for 85% power. For 90% power, increase the sample size by 17%. Table 6 displays the probabilities of being in different categories of the ordinal scale under an odds ratio of 2.

Table 4: Four scenarios considered for outcomes under placebo for sample size determination

	Anticipated
Severity Outcome	outcome
	(%)
Death	2
Hospitalised, on	
mechanical ventilation or ECMO	1

Hospitalised, on non- invasive ventilation or high flow oxygen Devices	2
Hospitalised, requiring supplemental oxygen	7
Hospitalised, not requiring supplemental	
Oxygen	8
Not hospitalised, limitation on activities	38
Not hospitalised, no limitations on activities	42

Table 5. Sample size calculations for scenarios in Table 4 for a two-arm trial assuming 85% power and various true odds ratios.

True odds ratio	Total sample size
1.5	774
1.75	412
2.0	272
2.25	201
2.5	159

Table 6. Treatment ordinal outcome proportions under odds ratio of 2 for scenario in Table 4 at day 15.

Anticipated						
Severity Outcome	Control %	Treatment %				
Death	2	1				
Hospitalised, on mechanical						
ventilation or ECMO	1	0.5				
Hospitalised, on non- invasive						
ventilation or high	2	1				
flow oxygen devices						
Hospitalised, requiring	7	3.8				
supplemental oxygen						
Hospitalised, not requiring	8	4.7				
supplemental oxygen						
Not hospitalised, limitation on	38	29.7				
activities						
Not hospitalised, no	42	59.2				
limitations on activities						

Note that columns may not sum to exactly 100 due to rounding errors.

Prior to the commencement of the trial, we took the anticipated WHO scenario and the odds ratio of 2 which required enrolment of 272 participants. Allowing for a potential loss to follow-up of 9% (27 participants) this meant we will required 300 participants (150 per arm) to achieve 85% power at 5% significance. This was subsequently reviewed as part of a pre-specified blinded sample size re-evaluation by an independent statistician. The results of this re-evaluation, using data for the primary endpoint available in December 2020 found that 300 patients enrolled would provide approximately 88% power to detect an odds ratio of 2.0. This, along with the results of other COVID-19 trials were reviewed by the Trial Steering Committee (TSC) and DMC who noted that other COVID-19 therapeutics had achieved odds ratios lower than 2.0 in the majority of cases. Based on this, the TSC and DMC recommended targeting an odds ratio of 1.75. At least 80% power for an odds ratio of 1.75 requires enrolment of a minimum of 360 patients with 400 patients provided approximately 85% power. A final sample size of 400 subjects was therefore recommended by the TSC and subsequently approved by the DMC in December 2020. Planned recruitment rate

Recruitment is expected to be completed by the end of January 2021.

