#### 7 General Considerations

## 7.1 Timing of Analyses

The final analysis will be conducted following last patient last visit assuming that at least 400 patients have been enrolled.

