## 7.4 Missing Data

(ICH E3; 9.7.1, 11.4.2.2. ICH E9;5.3. EMA Guideline on Missing Data in Confirmatory Clinical Trials)

All reasonable efforts will be taken to minimise loss to follow-up, which is expected to be minimal as data collection for primary and secondary outcomes using trial-specific eCRFs is combined with linkage to routine clinical data on study outcomes. The number and percentage of participants with follow-up information at day 29 after the randomisation will be reported. For all participants who were discharged and alive but have missing clinical status, a clinical status scale of 2 (Not hospitalised, limitation on activities) will be applied.

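### Do the revised power figures for 360 and 400 patients leave out the 9% loss to follow-up?

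*Protocol*

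**What the plan says.** Protocol 10.1 builds the original sample size in two steps. Table 5, headed as calculations "for a two-arm trial assuming 85% power and various true odds ratios", gives 272 at an odds ratio of 2.0 and 412 at 1.75. The text takes the first of these, "which required enrolment of 272 participants", and raises it to 300: "Allowing for a potential loss to follow-up of 9% (27 participants").

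The paragraph then reports a blinded re-evaluation by an independent statistician, "using data for the primary endpoint available in December 2020 found that 300 patients enrolled would provide approximately 88% power" at an odds ratio of 2.0. The steering and monitoring committees moved the target to 1.75, for which at least 80% power "requires enrolment of a minimum of 360 patients with 400 patients provided approximately 85% power". SAP 6 repeats the paragraph and refers to an Appendix 1. Protocol 10.1 calls itself a brief summary and leaves detail to an interim evaluation analysis plan. Neither of those is in the text available for review.

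SAP 7.1 ties the final analysis to enrolment, "assuming that at least 400 patients have been enrolled". SAP 7.4 says "All reasonable efforts will be taken to minimise loss to follow-up, which is expected to be minimal", citing linkage to routine clinical data. For participants discharged alive with no recorded status, "a clinical status scale of 2 (Not hospitalised, limitation on activities) will be applied".

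**The concern.** Three features suggest that the loss allowance was dropped when the target changed.

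- Loss is applied visibly to 272, but no loss rate accompanies 360 or 400. The word enrolment does not settle it, because the paragraph also uses it for the uninflated 272.
- Table 5 requires 412 for 85% power at 1.75 before any loss. The plan enrols 400 and claims about 85%.
- Rescaling 412 to 80% power gives 360.2, which is the stated minimum. On Table 4, both revised figures match the result with no loss.

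These figures justify the final sample size. If 9% loss still applied to a Table 4 population, 400 enrolled would have about 80.6% power, not 85%. The 360 minimum would have about 76.5%.

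**Working it through.** **Inputs.** Two-sided 5% significance (Protocol 10.2); 1:1 allocation (Protocol 7.4); placebo distribution, best to worst, of 42, 38, 8, 7, 2, 1 and 2% (Protocol 10.1, Table 4); Whitehead's proportional-odds method, cited in Protocol 10.1.

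**Formula.** N = 12(z₀.₉₇₅ + z_power)² / [(ln OR)² f], where f = 1 − Σp̄³ and p̄ is the mean of the two arms' category proportions. Inverted, power = Φ(√(Nf/12) × ln OR − 1.960). Table 4 gives f = 0.840 at OR 1.75 and 0.831 at OR 2.0.

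**Step 1: reproduce Table 5.** At OR 1.75 and 85% power, 12 × (1.960 + 1.036)² / (0.5596² × 0.840) = 409.5, against 412 printed. The other rows give 771.5, 269.7, 199.0 and 157.4, against 774, 272, 201 and 159. The loss step is 272/0.91 = 298.9, printed as 300.

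**Step 2: the revised figures on Table 4, OR 1.75.**

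| Assumed loss | 360 enrolled | 400 enrolled |
|---|---|---|
| 0% | 80.2% | 84.2% |
| 2% | 79.4% | 83.4% |
| 5% | 78.2% | 82.3% |
| 9% | 76.5% (328 evaluable) | 80.6% (364 evaluable) |

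Simulation of a tie-corrected Wilcoxon test gave 80.1% and 83.9% with no loss, and 76.1% and 80.0% with 9% loss. Anchoring on the printed 412 in place of 409.5 gives 84.0% at 400.

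**Step 3: test Table 4 with 9% loss against the 88% in the same paragraph.** At OR 2.0, 300 evaluable give 88.5%. With 9% lost, 273 evaluable give 85.4%. The re-evaluation reports about 88% for 300 enrolled, so the pairing behind 76.5% and 80.6% does not reproduce the one re-evaluation result that is printed.

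**Step 4: scale from the reported 88%.** With loss rate L, power depends on N(1 − L)f. The 88% fixes the product:

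(1 − L)f = 12 × (1.960 + 1.175)² / (0.6931² × 300) = 0.818

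Holding that product at OR 1.75 gives 79.2% at 360 and 83.2% at 400. L never has to be known. Two small allowances apply. First, f rises slightly at the smaller odds ratio; on Table 4 the ratio is 0.840/0.831 = 1.011. Second, approximately 88% may be anything from 87.5 to 88.5%. With both allowances, the range is 79.0 to 80.2% at 360 and 83.0 to 84.2% at 400.

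**Step 5: can the figures already include 9% loss?** Yes, if the December 2020 outcomes were more evenly spread. As an assumed example, a placebo distribution of 30, 34, 8, 9, 4, 5 and 10% has f = 0.913 at OR 1.75. With 9% loss it gives 88.3% (300 enrolled, OR 2.0), 79.8% (360) and 83.8% (400). This fits about as well as Table 4 with no loss.

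**The case for a change.** The strongest case for a change is that two readings fit the stated powers, and neither Protocol 10.1 nor SAP 6 lets the reader choose between them. Minimal is not a rate, and nothing says that the 9% was withdrawn. All three re-evaluation figures match Table 4 with no loss, so an oversight is plausible. The 360 minimum has no margin: on Table 4, 80% power needs 358.0 evaluable, so a third loss takes it below. Stating the inputs would cost only a few sentences.

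It stands that the pooled distribution and loss rate behind the 88, 80 and 85% are not printed in these sections, and that 400 is a little short of Table 5's 412. The inference of an omission does not stand. The 9% and Table 4 are both pre-trial assumptions, and the protocol itself calls the latter highly uncertain; the revised figures rest on later data. A loss of 9% is also pessimistic for this endpoint. Death is a category of the scale, and participants discharged alive with missing status stay in the analysis as category 2. At 2 to 5% loss on Table 4, 400 enrolled still has 82.3 to 83.4%. The thin margin at 360 concerns a number that was not adopted.

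**Conclusion.** The concern does not hold as an arithmetic error. The three re-evaluation figures agree with one another per enrolled patient: the 88% at 300 implies about 79 to 80% at 360 and 83 to 84% at 400. At most, the plan rounds up by one or two points, and 400 is better described as about 84%. This rests on the proportional-odds formula, which reproduces Table 5 to within three patients, and on the same loss rate lying behind all three figures.

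The unprinted inputs are missing reporting detail, and the documents point to two places that may hold them. Printing them would help a reader, but would change neither the 400 patients nor the analysis. Even in the least favourable case considered, Table 4 with 9% loss, 400 enrolled keeps about 80% power. No change to the plan follows.

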10.2. Statistical analysis plan

The primary analysis will be based on an intention-to-treat population, including participants randomized. Similarly, safety analyses will be based a modified intent-to-treat population consisting of all participants who were randomized.

This is a controlled randomized trial testing a superiority hypothesis with a two-sided type I error rate of 0.05. Secondary hypotheses have been ordered according to relative importance. These will be described according to the appropriate summary statistics (e.g., proportions for categorical data, means with 95% confidence intervals for continuous data, median for time-to-event data).

A statistical analysis plan (SAP) will be prepared for analysis of primary and secondary outcomes and will include a plan for handling missing data.

10.2.1. Summary of baseline data and flow of participants

Detailed in SAP

10.2.2. Primary outcome analysis

Detailed in SAP

10.2.3. Secondary outcome analysis

Detailed in SAP

10.3. Subgroup analyses

Detailed in SAP

10.4. Adjusted analysis

Detailed in SAP

10.5. Interim analysis and criteria for the premature termination of the trial

For reasonable cause, the PI may terminate a participant's participation in the trial prematurely. The Sponsor may decide to terminate the trial prematurely. If this occurs, written notification of the trial

termination is required to be sent to all the sites. Some conditions that may warrant trial termination include the following:

- · Discovery of an unexpected, significant, or unacceptable risk to the participants in the trial,
- Decision on the part of the funder to suspend or discontinue development of the investigational product,
- Decision by a regulatory authority or the Sponsor to stop the trial at any time, were applicable.

If the trial is prematurely terminated, all participants who received a dose of any of the trial drugs and have not completed their trial period will be discontinued from the trial drug immediately; all the safety procedures required to be performed will be conducted. All discontinued participants will be followed up by a phone call 30 days after discontinuation for collection of AEs. The Sponsor will notify the appropriate Regulatory bodies in the respective countries regarding the reason for terminating the trial.

The DMC will evaluate the results of the trial in an unblinded fashion for safety. Participant population

The participant populations whose data will be participated to the trial analysis – both for the primary analysis and any applicable secondary analyses will be all-treated population, i.e. any participant randomised into the trial that received at least one dose of trial drug. Procedure(s) to account for missing or spurious data will be detailed in the SAP.

The primary analysis will be based on the intention-to-treat principle. The extent of missing data will be examined and the reason for drop-out ascertained. Multiple imputation may be used to impute missing values if necessary and where assumptions for missing at random data are met. Where imputation is used, a sensitivity analysis will be conducted considering only cases without missing data. Complete case analysis where missing participants are excluded will be carried out as a secondary analysis.

10.6. Economic evaluation

No economic evaluation is planned.

11. DATA MANAGEMENT

11.1. Data collection tools and source document identification

Medical records will be used as source data. The EQ-5D (interviewer administration) will be completed by the research staff and act as source data, the completed form will be filed in the medical notes. All trial data relevant to a participant's general medical history will be recorded in the medical record. The medical record will be flagged to state that the patient is participating in the STOP-COVID19 trial.

The PI or delegate will maintain source documents for each participant in the trial, consisting of hospital medical records containing demographic and medical information, laboratory data, electrocardiograms, trial questionnaires and the results of any other tests or assessments.

An eCRF, using CASTOR Electronic Data Capture system, will be provided by TCTU. The trial system will be based on the protocol for the trial. Development and validation of the trial database and quality control will be done according to TCTU procedures.

The eCRF will not collect more information than is required to meet the aims of the trial and to ensure the eligibility and safety of the participant.

The PI may delegate eCRF completion but is responsible for completeness, plausibility and consistency of the eCRF. Delegated trial staff will enter the data required by the protocol into the eCRFs following training in the definitions and methods used in completing the eCRF. Any queries will be resolved by the

CI or delegated member of the trial team. On completion of data collection the PI must certify that the data entered into the eCRFs are complete and accurate. PI sign off of the eCRF will be embedded in the eCRF with the PI using their own login.

Data verification and cleaning and extraction of data will be performed as per TCTU local procedures and detailed in the Data Management Plan.

Data preservation and sharing will be in accordance with established procedures at the University of Dundee. General laboratory data methods and results will be documented in laboratory notebooks and then analysed and written up for publication for dissemination to the scientific community (Tayside only). All electronic data will be stored on secure University of Dundee or cloud-based servers which are have restricted access and have disaster recovery systems in place.

